13.10 Ancillary Studies

We will assess the following translational endpoints for this study.

- To compare the anti-MUC1 antibody titer at the time of surveillance colonoscopy to evaluate the anti-MUC1 antibody response in relation to adenoma recurrence. Since surveillance colonoscopy is generally at 3 years after an advanced adenoma, this titer will typically be obtained at approximately week 156.
- To evaluate MUC1 expression on baseline advanced adenomas and on recurrent adenomas detected at surveillance colonoscopy. Based on current knowledge of MUC1 expression and function in tumor cells, MUC1 negative adenomas are not expected to grow as immune escape variants, but this has never been tested before and the trial will provide an appropriate setting to study this issue.
- To evaluate levels of circulating myeloid derived suppressor cells (MDSC) in the vaccinated and the placebo group and correlate with anti-MUC1 antibody levels and adenoma recurrence.
- To establish a biospecimen repository archive including live cells, plasma, and germline DNA for future immunologic and other assays, for testing not currently accommodated within the budget of this trial.

Analysis of these translational endpoints:

Laboratory measures will be correlated with participant outcome (i.e., adverse events, IgG levels, etc.) and with each other as well. Cut-points will be determined based on previously defined and accepted standards. Descriptive statistics and simple scatter plots will be generated to review the continuous biomarker data. In addition, for continuous biomarker values, the actual and % change in the level of each of the biomarkers from baseline to post-baseline time points will be explored within each arm using Wilcoxon signed rank tests, and paired sample t-tests. Comparisons between MUC1 and placebo will be performed using a two-sample t-test or Wilcoxon rank sum test, as appropriate. All categorical variables will be analyzed using chi-square tests or Fisher's exact test. For all translational endpoints, any notable statistical result will be viewed as an impetus for further study rather than as a definitive finding in and of itself.

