2.4 Studies Planned in the Proposed Trial

Evaluation of anti-MUC1 antibody titer and MUC1 expression in adenomas in relation to adenoma recurrence

Anti-MUC1 IgG will be measured at w12 and w55 to measure the immune response to the vaccine in comparison to placebo, and at the time of the endpoint surveillance colonoscopy to examine the relationship between antibody titer and adenoma recurrence. In addition, sections of the qualifying advanced adenoma and of any recurrent adenomas will be obtained. Comparison of tumor associated

MUC1 antigen expression on the recurrent adenomas in relation to antibody response, and comparison among vaccine responders, non-responders, and the control group are planned.

Evaluation of anti-MUC1 antibody responses and pre-vaccination levels of circulating MDSC

Heparinized blood will be collected at week 0, 2, 10, and 12 and live PBMCs stored in DMSO and LN2 at -70 to -80°C. We plan measurements of levels of circulating MDSC in all participants. We know from the feasibility study that higher levels of MDSC were associated with lack of generation of vaccine induced antibodies. We will confirm this observation in a larger number of individuals and will evaluate MDSC levels as a variable influencing adenoma recurrence. In the placebo group, we expect to have MDSC low and MDSC high individuals in whom we can determine if adenoma recurrence rates might correlate with MDSC.

Using samples stored in the biorepository, eventually, stored PBMCs will be used to evaluate MUC1 specific T helper and CTL responses. These studies are more time intensive and expensive and funding for them will have to be obtained through other sources or other NCI grants. We do not anticipate difficulty obtaining funding for sophisticated immune assessments on this unique collection of clinical samples among participants undergoing a randomized trial of immunotherapy in a prevention setting. Within this trial, we are using T dependent antibody responses and T dependent memory responses as a surrogate marker of vaccine elicited T cells.

Placebo Response

There are several important reasons to include a placebo group. We do not know the frequency of spontaneous acquisition of antibodies to MUC1, nor do we have data on the natural history of fluctuation in antibody level over time. A control group with which to compare the antibody response and a control group with which to compare adenoma recurrence is essential.

Exclusion of Individuals with Cancer

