6.8.2 Registration/Randomization

6.8.2.1 Fax to [contact] a completed Eligibility Checklist (see CRF packet) to the CPN Registration Office between 8:00 a.m. and 4:30 p.m. Central time, Monday through Friday.

6.8.2.2 Randomization: For details, see Section 13.2.

6.8.2.3 Intervention on this protocol must commence at a CPN institution under the supervision of a CPN clinician.

6.8.2.4 Intervention cannot begin prior to Registration/Randomization and must begin \leq 14 days after Registration/Randomization.

6.8.2.5 Pathology and colonoscopy reports confirming diagnoses must be sent \leq 30 days post Registration/Randomization to the CPN QAS at CPN Operations Office, [name]; or [contact], Attention CPN QAS.

6.8.2.6 Once the intervention assignment has been ascertained by the CPN Registration Office, the appropriate blinded study agent information (MUC1 vaccine or placebo/saline injection) will be communicated to the designated data manager/nurse/pharmacist at the participant's Participating Organization. The name of this contact person is to be entered in the designated space on the eligibility checklist so the Registration Office personnel have it for each participant at the time of registering/randomizing the participant. Make sure this contact person will be available at the time of the registration so he or she can receive the information from the Registration Specialist. This contact person may not be involved in assessing adverse events or any other outcome measure and should not be the same person listed on page one of the eligibility checklist form as the person completing the form. The last page of the eligibility checklist form should provide the source of communication for the contact person, either fax or email, and the appropriate contact information.

6.8.2.7 Stratification Factors:

- Number of advanced adenoma on qualifying colonoscopy: ≥ 3 vs. < 3
- Gender: male vs. female

After the participant has been registered on to the study, values of the stratification factors will be recorded. Randomization will be performed by CPN personnel. The CPN electronic-based randomization system will be utilized to ensure that randomization of participants to appropriate study arms while balancing the stratification variables is carried out successfully.

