10.2.3 Tissue Specimens

Paraffin blocks and/or unstained slides from the polyps/adenomas removed during routine colonoscopy, pre- and post-intervention, will be requested from the institution at which the procedure was performed.

Tissue paraffin sections will be deparaffinized by baking overnight at 59°C. Endogenous peroxidase activity will be eliminated by treatment with 30% H₂O₂ for 15 min at room temperature. Antigen retrieval will be performed by microwave heating in 0.1% citrate buffer. Nonspecific binding sites will be blocked with Protein Blocking Agent (Thermo-Shandon Corp). Sections will be immunostained with anti-MUC1 antibody HMPV, which recognizes all forms of MUC1 by binding the epitope APDTR in the VNTR region in a glycosylation-independent manner (BD Pharmingen) and anti-MUC1 antibody VU-4H5 (Santa Cruz Biotechnology), which recognizes the epitope APDTRPAP in the VNTR region of hypoglycosylated MUC1 (Santa Cruz Biotechnology). Staining will be performed by the avidin-biotin peroxidase complex (ABC) method with a commercial kit (Vectastain ABC kit, Vector Laboratories). Color development will be performed by 3,3'-Diaminobenzidine (DAB) kit (BD Pharmingen).

Institutions that are unable to submit paraffin blocks may send five 5-micron unstained slides from each advanced adenoma as an alternative. Paraffin blocks and/or slides must be labeled with the participant ID number, specimen type, specimen number, and date of collection. Every effort must be made to make certain the specimen number on the block and/or slide labels corresponds to the polyp or adenoma number reported on the Colonoscopy Report CRF.

Send blocks/slides to:

CPN PC Office (Study MAY2013-01-01)
[name]
[name]

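### Section 13.10 gives no paired or clustered method for categorical MUC1 status: chi-square or Fisher's exact test would ignore the baseline-recurrent pairing if expression is dichotomised

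*Combined protocol and SAP*

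**What the plan says.** Section 13.10 lists among its translational endpoints: "To evaluate MUC1 expression on baseline advanced adenomas and on recurrent adenomas detected at surveillance colonoscopy". For continuous biomarkers it gives signed rank and paired t-tests for change within each arm, and a two-sample t-test or rank-sum test between arms. For the rest it says only: "All categorical variables will be analyzed using chi-square tests or Fisher's exact test". It states no significance level, unit of analysis or MUC1 positivity threshold. It adds that a notable translational result would prompt further study and would not count as a definitive finding.

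The tissue comes from the same people at two times. Section 2.4 says "sections of the qualifying advanced adenoma and of any recurrent adenomas will be obtained", and plans to compare "MUC1 antigen expression on the recurrent adenomas in relation to antibody response, and comparison among vaccine responders", non-responders and controls. Section 10.2.3 asks sites to ensure that "the specimen number on the block and/or slide labels corresponds to the polyp or adenoma number reported on the Colonoscopy Report CRF", so specimens are identified lesion by lesion. Section 6.8.2 stratifies on "Number of advanced adenoma on qualifying colonoscopy" (three or more against fewer), so more than one qualifying lesion per person is foreseen. The escape hypothesis in Section 13.10 is worded in categories: "MUC1 negative adenomas are not expected to grow as immune escape variants".

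**The concern.** Chi-square and Fisher's exact test assume independent observations. Two features of the MUC1 tissue data can break that assumption, and they affect different comparisons.

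- **Pairing.** Whether lesions turn from MUC1-positive to MUC1-negative is a question of change within a person. Comparing the baseline and recurrent percentages as two separate samples discards the link. If status is positively correlated within people, the test is conservative and loses power, and few pairs are available.
- **Clustering.** If one person contributes several recurrent adenomas and each is counted as a separate observation between arms, or between responders and non-responders, a few people with many polyps can drive the result. The test is then too liberal.

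Section 13.10 recognises within-person change for continuous biomarkers but offers nothing equivalent for categorical ones. At stake is what can be learned from a small tissue set that cannot be collected again.

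**Working it through.** **Step 1. How many people can supply recurrent tissue?** Section 13.5 assumes 45 evaluable per arm. I first reproduced its power table with the one-sided 0.05 pooled two-proportion test. For 45 vs 20%:

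- Pooled proportion 0.325; null SE = sqrt(2 × 0.325 × 0.675 / 45) = 0.0987.
- Alternative SE = sqrt((0.45 × 0.55 + 0.20 × 0.80) / 45) = 0.0952.
- z = (0.25 − 1.645 × 0.0987) / 0.0952 = 0.92, so power is 82.1% (plan: 82%).

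The other rows give 79.8% (plan: 79%) and 85.4% (plan: 85%). Expected participants with a recurrence:

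- 50 vs 25%: 45 × 0.75 = 33.75
- 45 vs 20%: 20.25 + 9 = 29.25
- 40 vs 15%: 45 × 0.55 = 24.75

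That is about 25 to 34 pairs with both arms pooled, if every block is obtained. I use 29 below. Because 13.10 gives no alpha, I take two-sided 0.05.

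**Step 2. Pairing, no true change.** With the same prevalence p at both times and within-person correlation rho, the variance of the difference is 2p(1−p)(1−rho)/n. The unpaired test uses 2p(1−p)/n. Its true type I error is therefore about 2[1 − Φ(1.96/√(1−rho))]: 2.8% at rho 0.2, 1.1% at 0.4 and 0.2% at 0.6. Simulation with 29 pairs, 60% positive at both times and rho 0.5 gave 0.5% for chi-square and 3.4% for mid-p McNemar.

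**Step 3. Pairing, assumed 70% positive at baseline and 40% at recurrence.** The proportion positive at both times is 0.7 × 0.4 + rho × sqrt(0.7 × 0.3 × 0.4 × 0.6) = 0.28 + 0.2245 rho. It cannot exceed 0.40, so rho cannot exceed 0.12/0.2245 = 0.53.

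- rho 0.5: both positive 0.392; positive to negative 0.308; negative to positive 0.008. Expected McNemar z = 29 × 0.30 / sqrt(29 × 0.316) = 2.9.
- rho 0.2: both positive 0.325; positive to negative 0.375; negative to positive 0.075. Expected McNemar z = 29 × 0.30 / sqrt(29 × 0.450) = 2.4.
- Unpaired chi-square, either rho: 0.30 / sqrt(2 × 0.55 × 0.45 / 29) = 2.3.

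Simulated power, 29 pairs:

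| rho | Chi-square | Fisher | Exact McNemar | Mid-p McNemar |
|---|---|---|---|---|
| 0.5 | 67% | 52% | 86% | 93% |
| 0.2 | 66% | 53% | 63% | 71% |

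An independent repeat gave chi-square 68% and mid-p 93% at rho 0.5, and chi-square 65%, mid-p 70% and exact McNemar 62% at rho 0.2. At rho 0.4, ordinary (asymptotic) McNemar has 79% against 65% for chi-square with 25 pairs, and 90% against 75% with 34.

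**Step 4. Clustering, no true difference.** Take 20 vs 9 recurring participants. With unequal lesion counts, the variance of a lesion-level proportion is inflated by D = 1 + (E[m²]/E[m] − 1) × ICC, and the true type I error is about 2[1 − Φ(1.96/√D)]. If m is 1 + Poisson, E[m²]/E[m] is 5/2 for a mean of 2 lesions and 11/3 for a mean of 3.

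| ICC | Mean 2: D, formula, simulated | Mean 3: D, formula, simulated |
|---|---|---|
| 0.05 | 1.075, 5.9%, 6.8% | 1.133, 6.6%, 7.0% |
| 0.2 | 1.30, 8.6%, 8.7% | 1.533, 11.3%, 12.5% |
| 0.5 | 1.75, 13.8%, 15.8% | 2.333, 20.0%, 20.7% |

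At ICC 0, a separate simulation over other group sizes gave chi-square 5.0 to 5.8%, which is no material inflation.

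Positivity, rho, ICC and lesions per person are assumptions in every step. The documents give none of them.

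**The case against.** A reader might infer that the plan's categorical tests have wrong error rates in both directions as a matter of fact. The documents do not support that.

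- **MUC1 status is not defined as binary.** The category appears only in the wording of the hypothesis. The background part of Section 2 describes expression as rising with the degree of dysplasia. If staining is scored on a continuous scale, 13.10 already provides paired tests. This stands, so the pairing point is conditional on dichotomising.
- **The sentence may mean between-arm comparisons only.** It follows directly on the sentence comparing vaccine with placebo. With one value per participant, chi-square or Fisher is then valid. This also stands. But on that reading the plan has no method at all for within-person categorical change.
- **No lesion-level test is planned.** Numbered specimens are sample tracking. The inflated false-positive rates describe an analysis that the plan leaves open and does not prescribe.
- **The large power gap is close to a best case.** A rho of 0.5 is just under the ceiling of 0.53. At 0.2 the gain over chi-square is about 5 points with mid-p McNemar, and exact McNemar gains nothing. With negative correlation (−0.2) chi-square becomes liberal, at 6.3 to 9.2% with 25 or 34 pairs.
- **The endpoint is exploratory.** Section 13.10 says so plainly. The caveat limits what may be claimed from a result, but it does not make an unpaired test suit paired data.

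**Conclusion.** The concern holds in a limited, conditional form. Section 13.10 leaves the unit of analysis for MUC1 status open and names no test for paired or clustered categorical data. Read literally, its rule for all categorical variables is the wrong one for a dichotomised baseline-versus-recurrent comparison.

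Under the 70% to 40% assumption with 29 pairs, the loss against mid-p McNemar runs from about 5 points of power at rho 0.2 to about 25 points at rho 0.5. Any inflation from clustering arises only if lesions are tested as independent and their status is correlated within people. It would then be about 6 to 7% at ICC 0.05 and roughly 14 to 21% at ICC 0.5, for an average of two to three adenomas each.

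This is a minor point. The primary endpoint, the key secondary endpoints and the decisions to proceed between Parts do not use this analysis.

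**What to change.** State how MUC1 staining is scored and, if it is dichotomised, the threshold. Then replace the sentence in 13.10 with wording to this effect:

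- Categorical variables with one value per participant are compared between groups by chi-square or Fisher's exact test.
- Baseline-versus-recurrent MUC1 status is analysed by mid-p McNemar, using one prespecified value per participant at each time, for example the qualifying advanced adenoma and the largest recurrent adenoma. Where there are several qualifying lesions, the plan should say which one is used.
- Any lesion-level comparison uses logistic GEE clustered on participant with a small-sample correction, or a participant-level summary that does not depend on lesion count, for example each person's proportion of MUC1-negative recurrent adenomas.

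Two simpler choices should be avoided. A summary such as any MUC1-positive recurrent adenoma rises with lesion count alone: at 60% positivity and independent lesions it is 1 − 0.4² = 84% with two and 1 − 0.4³ = 94% with three. It also does not address MUC1-negative escape. Uncorrected cluster-robust methods are slightly liberal with so few people: a cluster-robust t-test ran at 5.3 to 7.0% in simulation at ICC 0.2 to 0.6.

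The cost is a few lines of analysis wording, with no extra participants, samples or visits. The downside is slightly wider intervals for lesion-level comparisons.

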14. ETHICAL AND REGULATORY CONSIDERATIONS

14.1 Form FDA 1572

Prior to initiating this study, the Protocol Lead Investigator at the Lead or Participating Organization(s) will provide a signed Form FDA 1572 stating that the study will be conducted in compliance with regulations for clinical investigations and listing the investigators, at each site that will participate in the protocol. All personnel directly involved in the performance of procedures required by the protocol and the collection of data should be listed on Form FDA 1572.

14.2 Other Required Documents

14.2.1 Current (within two years) CV or biosketch for all study personnel listed on the Form FDA 1572 and Delegation of Tasks form for the Lead Organization and all Participating Organizations.

14.2.2 Current medical licenses (where applicable) for all study personnel listed on Form FDA 1572 and Delegation of Tasks form for the Lead Organization and all Participating Organizations.

14.2.3 Lab certification (*e.g.*, CLIA, CAP) and lab normal ranges for all labs listed on Form FDA 1572 for the Lead Organization and all Participating Organizations.

14.2.4 Documentation of training in “Protection of Human Research Subjects” for all study personnel listed on the FDA Form 1572 and Delegation of Tasks form for the Lead Organization and all Participating Organizations.

14.2.5 Documentation of Federalwide Assurance (FWA) number for the Lead Organization and all Participating Organizations.

14.2.6 Signed Investigator’s Brochure/Package Insert acknowledgement form.

14.2.7 Delegation of Tasks form for the Lead Organization and all Participating Organizations signed by the Principal Investigator for each site and initialed by all study personnel listed on the form

14.2.8 Signed and dated NCI, DCP Financial Disclosure Form for all study personnel listed on Form FDA 1572 for the Lead Organization and all Participating Organizations

14.3 Institutional Review Board Approval

Prior to initiating the study and receiving agent, the Investigators at the Lead Organization and the Participating Organization(s) must obtain written approval to conduct the study from the appropriate IRB. Should changes to the study become necessary, protocol amendments will be submitted to the DCP PIO according to DCP Amendment Guidelines. The DCP-approved amended protocol must be approved by the IRB prior to implementation

14.4 Informed Consent

All potential study participants will be given a copy of the IRB-approved Informed Consent to review. The investigator will explain all aspects of the study in lay language and answer all questions regarding the study. If the participant decides to participate in the study, he/she will be asked to sign and date the Informed Consent document. The study agent(s) will not be released to a participant who has not signed the Informed Consent document. Participants who refuse to participate or who withdraw from the study will be treated without prejudice.

Participants must be provided the option to allow the use of blood samples and tissues obtained during testing, operative procedures, or other standard medical practices for further research purposes. If applicable, statement of this option may be included within the informed consent document or may be provided as an addendum to the consent.

Prior to study initiation, the informed consent document must be reviewed and approved by NCI, DCP, the Consortium Lead Organization, and the IRB at each Organization at which the protocol will be implemented. Any subsequent changes to the informed consent must be approved by NCI, DCP, the Consortium Lead Organization's IRB, and then submitted to each organization's IRB for approval prior to initiation.

14.5 Submission of Regulatory Documents

All regulatory documents are collected by the Consortia Lead Organization and reviewed for completeness and accuracy. Once the Consortia Lead Organization has received complete and accurate documents from a participating organization, the Consortium Lead Organization will forward the regulatory documents to the DCP Regulatory Contractor:

Paper Document/CD-ROM Submissions:

Regulatory Affairs Department
CCS Associates
[name]
[name]
[contact]
[contact]

E-mail Submissions: [contact]

Regulatory documents that do not require an original signature may be sent electronically to the Consortium Lead Organization for review, which will then be electronically forwarded to the DCP Regulatory Contractor.

14.6 Other

This trial will be conducted in compliance with the protocol, Good Clinical Practice (GCP), and the applicable regulatory requirements.

APPENDIX A

Performance Status Criteria

ECOG Performance Status Scale		Karnofsky Performance Scale	
Grade	Descriptions	Percent	Description
0	Normal activity. Fully active, able to carry on all pre-disease performance without restriction.	100	Normal, no complaints, no evidence of disease.
		90	Able to carry on normal activity; minor signs or symptoms of disease.
1	Symptoms, but ambulatory. Restricted in physically strenuous activity, but ambulatory and able to carry out work of a light or sedentary nature (e.g. , light housework, office work).	80	Normal activity with effort; some signs or symptoms of disease.
		70	Cares for self, unable to carry on normal activity or to do active work.
2	In bed <50% of the time. Ambulatory and capable of all self-care, but unable to carry out any work activities. Up and about more than 50% of waking hours.	60	Requires occasional assistance, but is able to care for most of his/her needs.
		50	Requires considerable assistance and frequent medical care.
3	In bed >50% of the time. Capable of only limited self-care, confined to bed or chair more than 50% of waking hours.	40	Disabled, requires special care and assistance.
		30	Severely disabled, hospitalization indicated. Death not imminent.
4	100% bedridden. Completely disabled. Cannot carry on any self-care. Totally confined to bed or chair.	20	Very sick, hospitalization indicated. Death not imminent.
		10	Moribund, fatal processes progressing rapidly.
5	Dead.	0	Dead.

